Visit 1 – Subjects will be randomized to receive Treatment A or Treatment B first for the initial 24 weeks. Subjects will receive MRI brain with and without gadolinium contrast utilizing MRI sequences as detailed in Stage 2a.

Subjects will be contacted by telephone or email monthly to document tolerability and encouraged to report any AE occurring with drug at any point during the study.

Visit 2 – Subjects will receive a complete medical and neurological examination, MSFC & EDSS evaluation as well as patient-reported clinical disability measures (MFIS & MSWS-12) and will be asked questions to ascertain tolerability to daily therapy. All subjects will obtain MRI brain without gadolinium contrast utilizing the sequences described above except for DSC sequence.

Visit 3 – Subjects will receive a complete medical and neurological examination, MSFC & EDSS evaluation as well as patient-reported clinical disability measures (MFIS & MSWS-12) and will be asked questions to ascertain tolerability to daily therapy. All subjects will obtain MRI brain with and without gadolinium contrast utilizing the sequences described above.

Visit 4 – Subjects will receive a complete medical and neurological examination, MSFC & EDSS evaluation as well as patient-reported clinical disability measures (MFIS & MSWS-12) and will be asked questions to ascertain tolerability to daily therapy. All subjects will obtain MRI brain

without gadolinium contrast utilizing the sequences described above except for DSC sequence.

Visit 5 – Subjects will receive a complete medical and neurological examination, MSFC & EDSS evaluation as well as patient-reported clinical disability measures (MFIS & MSWS-12) and will be asked questions to ascertain tolerability to daily therapy. All subjects will obtain MRI brain with and without gadolinium contrast utilizing the sequences described above.

Upon completion of the MRI scan, subjects previously treated with Treatment B will start Treatment A and all subjects will continue on Treatment A for the remaining 24 weeks of the study.

Visit 6 – Subjects will receive a complete medical and neurological examination, MSFC & EDSS evaluation as well as patient-reported clinical disability measures (MFIS & MSWS-12) and will be asked questions to ascertain tolerability to daily therapy. All subjects will obtain MRI brain with and without gadolinium contrast utilizing the sequences described above.

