Visit 7 – Subjects will receive a complete medical and neurological examination, MSFC & EDSS evaluation as well as patient-reported clinical disability measures (MFIS & MSWS-12) and will be asked questions to ascertain tolerability to daily therapy. All subjects will obtain MRI brain without gadolinium contrast utilizing the sequences described above except for DSC sequence.

Visit 8 – Subjects will receive a complete medical and neurological examination, MSFC & EDSS evaluation as well as patient-reported clinical disability measures (MFIS & MSWS-12) and will be asked questions to ascertain tolerability to daily therapy. All subjects will obtain MRI brain with and without gadolinium contrast utilizing the sequences described above.

Visit 9 – Subjects will receive a complete medical and neurological examination, MSFC & EDSS evaluation as well as patient-reported clinical disability measures (MFIS & MSWS-12) and will be asked questions to ascertain tolerability to daily therapy. All subjects will obtain MRI brain without gadolinium contrast utilizing the sequences described above except for DSC sequence.

Visit 10 – Subjects will receive a complete medical and neurological examination, MSFC & EDSS evaluation as well as patient-reported clinical disability measures (MFIS & MSWS-12) and will be asked questions to ascertain tolerability to daily therapy. All subjects will obtain MRI brain with and without gadolinium contrast utilizing the sequences described above. Upon completion of the brain MRI, all subjects will be instructed to discontinue assigned treatment.

Visit 11 – Subjects will receive a complete medical and neurological examination, MSFC & EDSS evaluation as well as patient-reported clinical disability measures (MFIS & MSWS-12) and will be asked questions to ascertain any other AEs after discontinuation of therapy. All subjects will obtain MRI brain without gadolinium contrast utilizing the sequences described above except for DSC sequence.

Subjects will be contacted by telephone or email monthly to document tolerability and encouraged to report any AE occurring with drug at any point during the study.

For any part of the study, a subject whose CBC or CMP is not at or near baseline values will repeat these blood tests.

a. Final Study Visit:

The final study visit will be used to document any potential adverse event associated with treatment arm, not previously documented.

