FDA approved extended release ACZ tablets from American Health will be used for "Treatment A". Commercially available placebo capsules manufactured by American Health composed entirely of lactose monohydrate filler that will be used for "Treatment B".

Study Drug Administration

"Treatment A" will be obtained directly from American Health and stored at MHHS pharmacy at Memorial Hermann Hospital. "Treatment B" is commercially available directly from American Health and will be shipped to MHHS pharmacy, shipped to CPHS pharmacy and stored. For stage 3, patients will be given either "Treatment A" or "Treatment B", based upon randomization, in sufficient quantities for each study visit. At the end of each study visit, patients will be asked to return any unused capsules. Unused capsules will be counted and stored in a secure facility at the McGovern Medical School, UTHealth.

Subjects with known hypersensitivity to sulfonamides or derivative drugs will be excluded from study participation (see section 3.4 for complete exclusion criteria). Subjects will be informed of common adverse reactions to sulfonamides including anaphylaxis, fever, rash (including erythema multiforme, Stevens-Johnson syndrome, toxic epidermal necrolysis), crystalluria, renal calculus, bone marrow depression, thrombocytopenic purpura, hemolytic anemia, leukopenia, pancytopenia and agranulocytosis. The drug will be discontinued and appropriate therapy instituted for any of these adverse reactions.

Specific Restrictions / Requirements

Subjects will be required to discontinue use of any frequently used over the counter medication, vitamin or other supplement one week prior to treatment with ACZ and for the duration of the study.

Blinding

Stage 1a to 2b are unblinded stages. Stage 3 is the only double-blinded portion of this study. Both subjects and raters will remain blinded to treatment randomization.Common AE such as paresthesias, particularly a "tingling" feeling in the extremities, and gastrointestinal disturbances such as nausea, vomiting and diarrhea typically occur early in treatment and might be more pronounced in subjects initially randomized to ACZ. Subjects will be encouraged to avoid disclosing any AE so as to maintain the blind for clinical rater(s). Imaging rater(s) will not have direct contact with study subjects and no potential for unblinding is present.

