A comprehensive list of AEs provides previously reported and/or potential AEs associated with ACZ. Common AEs are in **bold**. They include **paresthesias**, particularly a "tingling" feeling in the extremities, hearing dysfunction or tinnitus, loss of appetite, **taste alteration** and gastrointestinal disturbances such as **nausea**, **vomiting**, **dyspepsia and diarrhea**, polyuria, and occasional instances of **drowsiness/fatigue** and confusion. Metabolic acidosis and electrolyte imbalance may occur. Transient myopia has been reported though this condition invariably subsides upon diminution or discontinuance of the medication.

Other occasional adverse reactions include urticaria, melena, hematuria, glycosuria, hepatic insufficiency, flaccid paralysis, photosensitivity and convulsions.

Collecting, Recording and Reporting of Adverse Events

Recording AEs – The treating physician will be the principal investigator ([name]). The treating physician will oversee subject management including all assessments and treatment of adverse events and disease relapses should they occur. The treating physician will make decisions regarding determining relatedness and grading severity of all AEs. The treating physician will be blinded to treatment arm unless necessary to assess safety concern.

Maintaining documentation and reporting AEs – The clinical coordinator ([name]) will assist in subject management, maintain documentation including all subject case report forms (unanticipated problems tracking log) and will submit all reports to the IRB per UTSHC-Houston policy

Safety Monitoring Plan

This pilot study will determine the extent to which improved cerebral perfusion from oral ACZ therapy reduces the evolution of MS lesion into permanent black hole. Subjects will be monitored, as per protocol, by the treating physician for clinical MS activity. However, to our knowledge there are no case reports or other studies to suggest that therapy with ACZ will contribute to new lesion formation or clinical relapse. As such, we do not anticipate an increase in relapse frequency secondary to ACZ.

Subjects will be monitored by the treating physician for AEs and serious AEs (see section 9.1). The frequency and grade of AEs will be documented and treatment arm(s) adjusted or discontinued as needed. Subjects can withdraw consent for study at any point and for any reason during the trial.

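### Stage 3 subjects are encouraged both to avoid disclosing any AE and to report any AE, with no recipient named and no exception for safety reporting

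*Combined protocol and SAP*

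**What the plan says.** All references are to the combined protocol and SAP.

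- **Treatment, Blinding.** "Stage 3 is the only double-blinded portion of this study", so the instruction concerns Stage 3. The section expects common AEs such as tingling and gastrointestinal upset, which "typically occur early in treatment and might be more pronounced in subjects initially randomized to ACZ". It then says: "Subjects will be encouraged to avoid disclosing any AE so as to maintain the blind for clinical rater(s".
- **End Points - Safety, and Stage 3 Visit 1.** In both places subjects are "encouraged to report any AE occurring with drug at any point during the study".
- **Stage 3 visits.** "Subjects will be contacted by telephone or email monthly to document tolerability". At Visits 2 to 10 subjects have the examination, the MSFC and EDSS and the patient-reported scales, and "will be asked questions to ascertain tolerability to daily therapy". Visit 11 asks about AEs after discontinuation.
- **Final Study Visit.** "The final study visit will be used to document any potential adverse event associated with treatment arm, not previously documented".
- **Collecting, Recording and Reporting of Adverse Events.** The treating physician decides relatedness and severity for all AEs, and a coordinator keeps the documentation. "The treating physician will be blinded to treatment arm unless necessary to assess safety concern".
- **Safety Monitoring Plan.** A three-member DSMB reviews all AEs.

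**The concern.** The Blinding sentence covers every AE and gives its reason, the clinical raters' blind, but does not say which person should not be told. A subject who follows it literally cannot also follow the reporting instruction. The Stage 3 visit text lists the rating and the tolerability questions together without assigning either to a person, so the subject has no way to tell which conversation is meant.

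Two things depend on subjects speaking up. The first is individual safety: withdrawal turns partly on symptoms known mainly from self-report, and the DSMB can review only what has been recorded. The second is the AE comparison itself: Stage 3 is the only placebo-controlled stage, and the contrast exists only in weeks 0-24, because the placebo group starts ACZ at week 24.

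**Working it through.** The plan gives no AE rate, disclosure rate or AE-based power calculation, so there is no figure to reproduce. The main check is a comparison of the texts.

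**1. The two instructions**

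| | Non-disclosure (Blinding) | Reporting (End Points - Safety; Stage 3 Visit 1) |
|---|---|---|
| Events covered | Any AE | Any AE occurring with drug |
| Who is addressed | Stage 3 subjects | The same subjects |
| Recipient named | No; only the purpose mentions clinical raters | Not in terms; linked to visits and monthly contacts |
| Exception for safety reporting | None | Not applicable |

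The written safety exception in the AE-recording section concerns unblinding the physician. It does not tell subjects what they may disclose.

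**2. Can a subject tell who must not hear?** A distinct blinded EDSS/MSFC rater is identified only under Stage 2b, which the Blinding section lists as unblinded. No Stage 3 text says that the rater differs from the treating physician or from the person asking about tolerability. Because the physician is also blinded, an instruction meant to protect a blind could be taken to cover the physician.

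**3. Which AEs depend on disclosure?** Laboratory AEs are found from test results whatever the subject says. Tingling, nausea and taste change are not. Monthly contacts, visit questions and the final visit all rely on the same instructed subject. The final visit is at week 50, which is 50 - 24 = 26 weeks after the placebo-controlled period ends.

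**4. Possible size (all rates assumed)**

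Let pA and pP be the true proportions with an AE on ACZ and placebo, and qA and qP the shares of affected subjects whose AE goes unrecorded.

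- Recorded difference = pA(1 - qA) - pP(1 - qP)
- Loss = pA·qA - pP·qP
- With equal q, the difference is multiplied by (1 - q), the risk ratio is unchanged, and the ACZ share of missed subjects in equal arms is pA/(pA + pP).

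| True % ACZ / placebo | True difference (points) | Recorded, q = 10% | q = 25% | q = 50% | Missed subjects on ACZ |
|---|---|---|---|---|---|
| 30 / 10 | 20 | 18 | 15 | 10 | 75% |
| 50 / 10 | 40 | 36 | 30 | 20 | 83% |
| 50 / 20 | 30 | 27 | 22.5 | 15 | 71% |
| 70 / 20 | 50 | 45 | 37.5 | 25 | 78% |

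Example for 50 / 10 with q = 25% in both arms: 0.75 × 50 = 37.5% and 0.75 × 10 = 7.5%. The difference is 30 points and the ratio 37.5/7.5 = 5.0, as it was before. With 60 subjects and an assumed 1:1 split, expected counts fall from 15 and 3 to 11.25 and 2.25.

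The ratio moves only if non-disclosure differs by arm. With 25% on ACZ and none on placebo, 50 / 10 becomes 37.5 / 10, a ratio of 3.75. If AEs are withheld only from the efficacy rater and reach the record by another route, q = 0 and nothing changes.

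**The case against.** The strongest reply is that the sentence limits itself through its stated purpose. It sits in a section about blinding, next to a sentence on imaging raters, and the surrounding rules make sense only if the study team hears about AEs: drug is stopped for listed reactions, patients are withdrawn for certain symptoms, and the physician grades every event. Silence towards the rater alone is therefore the coherent reading. There are also several capture routes: monthly contacts, visit questions, Visit 11, the final visit and blood tests. Finally, the complaint turns on what subjects are told, and the consent text was not available to this review.

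Much of this stands. A reader might infer that AEs will be under-counted, and mostly on ACZ. The documents do not support that. The capture routes may work, no rates are given, and the plan says only that AEs might be more pronounced on ACZ. In the illustration, the larger number missed on ACZ follows from assuming more AEs there. Nor should one argue that tolerability is a Stage 3 objective: it is a stated purpose of Stages 2a and 2b, and for Stage 3 the relevant text is the safety end point and DSMB review.

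What the reply does not remove is the wording. The rater-only reading has to be inferred by someone who knows the staff roles, and the Stage 3 text does not set those roles out. Apart from laboratory tests, the capture routes depend largely on the subject being willing to speak.

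**Conclusion.** The conflict in wording is real and should be corrected. Read literally, the Stage 3 instruction may discourage reporting of symptomatic AEs, which could weaken the withdrawal rules and DSMB review and shrink the weeks 0-24 difference in AE proportions. The amount is unknown. It ranges from zero, if silence is kept only towards the efficacy rater, to a proportional loss of q in the risk difference if a share q of affected subjects in both arms goes unrecorded. A distorted risk ratio would require non-disclosure to differ by arm, and nothing in the documents shows that it would. The primary CBF analysis and its sample size are not affected.

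**What to change.** Reword the Blinding sentence and the matching subject instructions to say three things:

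- Subjects should not discuss possible drug effects with the EDSS/MSFC rater, and this applies to that rater only.
- Every AE is to be reported to the treating physician or coordinator.
- Non-disclosure never applies to safety reporting.

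In the Stage 3 visit text, assign the tolerability questions, among existing staff, to someone other than the EDSS/MSFC rater, and state that separation. Then reconcile End Points - Safety, the Stage 3 visits, Final Study Visit, Blinding, and the AE-recording section.

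This keeps the rater's blind and changes no dose, withdrawal rule, endpoint or sample size. The cost is a small wording change. If one person now does both tasks, some visit work must also be reallocated; the documents do not show whether that is so.

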Fatalities have occurred, although rarely, due to severe reactions to sulfonamides including Stevens-Johnson syndrome, toxic epidermal necrolysis, fulminant hepatic necrosis, agranulocytosis, aplastic anemia, and other blood dyscrasias. Sensitizations may recur when a sulfonamide is readministered irrespective of the route of administration. If signs of hypersensitivity or other serious reactions occur, discontinue use of this drug. Caution is advised for patients receiving concomitant high-dose aspirin an acetazolamide, as anorexia, tachypnea, lethargy, coma and death have been reported.

PRECAUTIONS

General

Increasing the dose does not increase the diuresis and may increase the incidence of drowsiness and/or paresthesia. Increasing the dose often results in a decrease in diuresis. Under certain circumstances, however, very large doses have been given in conjunction with other diuretics in order to secure diuresis in complete refractory failure.

Information for Patients

Adverse reactions common to all sulfonamide derivatives may occur: anaphylaxis, fever, rash (including erythema multiforme, Stevens-Johnson syndrome, toxic epidermal necrolysis), crystalluria, renal calculus, bone marrow depression, thrombocytopenic purpura, hemolytic anemia, leukopenia, pancytopenia and agranulocytosis. Precaution is advised for early detection of such reactions and the drug should be discontinued and appropriate therapy instituted.

In patients with pulmonary obstruction or emphysema where alveolar ventilation may be impaired, acetazolamide which may precipitate or aggravate acidosis, should be used with caution. Caution is advised for patients receiving concomitant high-dose aspirin and acetazolamide, as anorexia, tachypnea, lethargy, coma and death have been reported (see **WARNINGS**).

Laboratory Tests

To monitor for hematologic reactions common to all sulfonamides, it is recommended that a baseline CBC and platelet count be obtained on patients prior to initiating acetazolamide therapy and at regular intervals during therapy. If significant changes occur, early discontinuance and institution of appropriate therapy are important. Periodic monitoring of serum electrolytes is recommended.

Carcinogenesis, Mutagenesis, Impairment of Fertility

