Caution is advised for patients receiving concomitant high-dose aspirin and acetazolamide, as anorexia, tachypnea, lethargy, metabolic acidosis, coma, and death have been reported.

PRECAUTIONS

General

Increasing the dose does not increase the diuresis and may increase the incidence of drowsiness and/or paresthesia. Increasing the dose often results in a decrease in diuresis. Under certain circumstances, however, very large doses have been given in conjunction with other diuretics in order to secure diuresis in complete refractory failure.

Information for Patients

Adverse reactions common to all sulfonamide derivatives may occur: anaphylaxis, fever, rash (including erythema multiforme, Steven-Johnson syndrome, toxic epidermal necrolysis), crystalluria, renal calculus, bone marrow depression, thrombocytopenic purpura, hemolytic anemia, leukopenia, pancytopenia, and agranulocytosis. Caution is advised for early detection of such reactions and the drug should be discontinued and appropriate therapy instituted.

In patients with pulmonary obstruction or emphysema where alveolar ventilation may be impaired, acetazolamide which may precipitate or aggravate acidosis should be used with caution. Gradual ascent is desirable to try to avoid acute mountain sickness. If rapid ascent is undertaken and acetazolamide is used, it should be noted that such use does not obviate the need for prompt descent if severe forms of high altitude sickness occur, i.e., high altitude pulmonary edema (HAPE) or high altitude cerebral edema.

Caution is advised for patients receiving concomitant high-dose aspirin and acetazolamide, as anorexia, tachypnea, lethargy, metabolic acidosis, coma, and death have been reported (see WARNINGS).

Both increases and decreases in blood glucose have been described in patients treated with acetazolamide. This should be taken into consideration in patients with impaired glucose tolerance or diabetes mellitus.

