Patients with intolerable paraesthesia, change in taste, accelerated change in blood pressure or fluid retention will be withdrawn from the study. Patients with persistent AEs will be referred to their primary care physician for continued monitoring and treatment using standard or care practices.

Concomitant therapy

Subjects will be encouraged to refrain from any over the counter medication, vitamin or other supplement including concomitant use of high-dose aspirin for analgesia. Subjects will be warned that an increased potential for serious AE has been reported in patients taking both ACZ and high-dose aspirin.

Subjects will be required, as stated in inclusion criteria (see section 3.3,) to be stable on any FDA-approved DMT.

SAFETY MEASUREMENTS

Definitions

The descriptions and grading scales found in the NCI Common Terminology Criteria for Adverse Events v 3.0 (CTCAE; published June 10, 2013) will be utilized for AE reporting.

Attribution of the AE:

- Definite The AE is clearly related to the study treatment
- Probable The AE is likely related to the study treatment
- Possible The AE may be related to the study treatment
- Unlikely The AE is doubtfully related to the study treatment
- Unrelated The AE is clearly NOT related to the study treatment

AEs should be recorded and graded 1 to 5 according to the CTCAE grades provided below:

- Grade 1 = Mild adverse event
- Grade 2 = Moderate adverse event
- Grade 3 = Severe and undesirable adverse event
- Grade 4 = Life-threatening or disabling adverse event
- Grade 5 = Death

For additional information, consult the National Cancer Institute's Common Terminology Criteria for Adverse Events v3.0 (published June 10, 2003) at the following URL: http://ctep.cancer.gov/reporting/ctc.html

An AE is defined as any untoward medical occurrence in a patient administered a pharmaceutical

product. Adverse events are to be recorded in the clinical chart. Severity, action taken, and relationship will be recorded as noted in the chart.

Serious Adverse Event (SAE) is defined as any untoward medical occurrence resulting in hospitalization or additional medical intervention in a patient administered a pharmaceutical product. SAE is to be recorded in the clinical chart. Severity, action taken, and relationship will be recorded as noted in the chart.

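### Occasional high-dose aspirin with acetazolamide is discouraged but not barred; a uniform prohibition would be a cheap safety gain

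*Combined protocol and SAP*

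**What the plan says.** Two sections under Treatment govern over-the-counter products.

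- Specific Restrictions / Requirements is mandatory but limited in scope. Subjects are "required to discontinue use of any frequently used over the counter medication, vitamin or other supplement one week prior to treatment with ACZ", and the rule runs through the end of the study.
- Concomitant therapy is wider but not mandatory: "Subjects will be encouraged to refrain from any over the counter medication, vitamin or other supplement including concomitant use of high-dose aspirin for analgesia". It continues: "Subjects will be warned that an increased potential for serious AE has been reported in patients taking both ACZ and high-dose aspirin".

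The inserts reproduced under Trial Materials address the same combination. The intravenous insert advises caution with high-dose aspirin, "as anorexia, tachypnea, lethargy, coma and death have been reported". The oral insert says: "Caution is advised for patients receiving concomitant high-dose aspirin and acetazolamide, as anorexia, tachypnea, lethargy, metabolic acidosis, coma, and death have been reported".

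On the blind, Recording AEs states: "The treating physician will be blinded to treatment arm unless necessary to assess safety concern". At Stage 3 Visit 5 (week 24), "subjects previously treated with Treatment B will start Treatment A and all subjects will continue on Treatment A for the remaining 24 weeks".

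The Drug Interactions part of the oral insert also advises against taking other carbonic anhydrase inhibitors together with ACZ.

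**The concern.** The one mandatory rule turns on frequency of use, and the one sentence that names high-dose aspirin has no force beyond encouragement and a warning. A subject who takes a high dose now and then for pain breaks no rule, yet the protocol's own reference text reports deaths with the combination.

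What is at stake is subject safety, not the validity of the cerebral blood flow comparison. During weeks 0 to 24 of Stage 3, the subject does not know whether ACZ is being taken, and normally neither does the treating physician, so a warning about combining the two drugs is hard to apply case by case. From week 24 every Stage 3 subject takes ACZ. A single rule for all subjects suits both periods and needs no unblinding.

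**Working it through.** The point is textual and the plan has no figure to reproduce. The check sets the rules side by side and then sizes the exposure and the cost.

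**1. The rules compared**

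| Place | Product covered | Force |
|---|---|---|
| Specific Restrictions / Requirements | Over-the-counter products in frequent use | Must stop |
| Concomitant therapy | Any over-the-counter product, high-dose aspirin named | Encouraged to refrain; warned |
| Exclusion Criteria | Aspirin not mentioned | None |
| IV and oral inserts | High-dose aspirin with ACZ | Caution; coma and death reported |

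The first two rows can be reconciled as tiers: frequent use must stop, other use is discouraged. On that reading frequent over-the-counter aspirin is already barred, and what remains open is occasional high-dose use.

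**2. How the sponsor treated similar advice.** Both inserts say that ACZ should be used with caution in pulmonary obstruction or emphysema. Exclusion 9 turns that into an outright exclusion. The aspirin advice is of the same grade, with deaths reported, but became encouragement only.

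**3. Dose.** The oral insert recommends 500 mg twice daily for glaucoma, or 1000 mg/day. The schedule tables give 1000 mg twice daily in Stage 2a (2000 mg/day, 2 times the label dose) and up to 2000 mg twice daily in Stage 1b (4000 mg/day, 4 times). Rationale for Doses Selected gives a lower Stage 1b ceiling of 1500 mg/day (1.5 times). The documents do not say how the interaction depends on ACZ dose.

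**4. Detection.** The reported interaction signs include anorexia and lethargy. The protocol's own adverse event list has loss of appetite and drowsiness or fatigue as ACZ effects, so early signs could pass for ordinary intolerance. In the Stage 1b table the metabolic panel is scheduled only at Day -7 and week 8, a gap of 8 − (−1) = 9 weeks, with none between dose steps. Clinical visits in that stage are every 2 weeks.

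**5. Exposure.** Oral-ACZ places at most: 10 (1b) + 10 (2a) + 10 (2b) + 60 (Stage 3) = 90. A subject may join more than one stage, so the number of persons may be lower.

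**6. Cost of one medication question**

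- Scheduled history-and-physical visits in the tables: 6 in Stage 1b, 5 in 2a, 6 in 2b, 10 in Stage 3. Total at most 10×6 + 10×5 + 10×6 + 60×10 = 60 + 50 + 60 + 600 = 770.
- Monthly contacts over 48 weeks come to about 11 to 12 per Stage 3 subject: 60×11 = 660 to 60×12 = 720.
- Together 770 + 660 = 1,430 to 770 + 720 = 1,490, before monthly contacts in Stages 1b to 2b.

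**7. Carbonic anhydrase inhibitors.** No readable eligibility or concomitant-therapy rule repeats the insert's advice. Exclusion 14 concerns conditions, not drugs. The criteria on glaucoma, renal disease and heart failure, and in Stage 3 other neurologic disease, reduce the chance of outside use but act only at entry. However, inclusion 4 is blank and exclusion 7, a drug list, has a gap in the available text. Either could contain the rule.

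**The case against.** The strongest reply is that the protocol already goes further than the label. The inserts ask for caution. The protocol stops frequent over-the-counter use, discourages the rest, names high-dose aspirin and warns about it. The inserts do not tie the reported deaths to occasional use. On this view, preferring a ban to a warning is a matter of taste. Safeguards also exist: blood counts and metabolic panels about every 6 weeks in Stages 2a to 3, repeat tests when results move from baseline, monthly contacts, independent review of all adverse events, and unblinding when safety requires it.

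Much of this stands. A reader might infer that the protocol breaches the label or lets subjects take aspirin freely. The documents support neither: the label does not contraindicate the combination, and frequent over-the-counter use must stop. A reader might also infer that Stage 1b is the least supervised stage. That holds only for the scheduled metabolic panel. The stage is unblinded, has an examination every 2 weeks and includes adverse event checks at each dose transition.

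What does not fall away is that the safeguards mainly detect harm after exposure, while the rule meant to prevent the combination leaves occasional use open. Closing it costs very little.

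**Conclusion.** The aspirin point holds as a worthwhile, low-cost safety change. It rests on reading the two sections as tiers. If Concomitant therapy were instead read as overriding the mandatory rule, the gap would be wider, but the text does not require that reading. Neither the protocol nor the inserts define high-dose aspirin.

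The size is up to 90 oral-ACZ places, with the blinded exposure confined to the 60 Stage 3 subjects in weeks 0 to 24. The documents give no rate of aspirin use and no risk per exposure, so no number of events is claimed.

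The carbonic anhydrase inhibitor point is secondary and conditional. It would be tempting to call the missing rule an error in the plan. The unreadable items prevent that conclusion, and the aspirin point does not depend on it. Nor do the documents support a claim that outside drug use would bias the blood flow results. Sample size, power and type I error are unaffected.

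**What to change.** 1. In Concomitant therapy, prohibit high-dose aspirin during study treatment in all oral ACZ stages and in both Stage 3 arms. The sponsor should define the dose and name a permitted analgesic.
2. Align that section with Specific Restrictions / Requirements: frequent over-the-counter use must stop, and other occasional over-the-counter use is discouraged. No wider ban is needed.
3. Check inclusion 4 and exclusion 7 in the source document. If they do not already cover it, add one line barring non-trial ACZ and other carbonic anhydrase inhibitors at entry and during the study.
4. Ask one medication question at existing history-and-physical visits and monthly contacts.

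The cost is protocol wording and the added questions (more than 770 in total once monthly contacts are counted), with no new visit or laboratory test. Analgesic choice is slightly restricted, and a few otherwise eligible patients may be excluded.
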